- Renal consult

6) Provider awareness outcomes

- Chart documentation of AKI (by post-discharge ICD-10 codes)
- Chart documentation of AKI (adjudicated)

Study Procedures

Randomization

Randomization will occur the moment AKI is detected by the electronic monitoring system within the EPIC best practice alert framework, as developed by JDAT. Beyond the primary intervention, no further tests or procedures will be performed on subjects in this trial. Randomization will be performed within the Epic system using a random number rule that is incorporated in the alert. This ensures that, upon meeting criteria, each patient is immediately and randomly assigned to an arm. Logic checks within the alerts ensure that once a patient is assigned to an arm, they remain on that arm for the remainder of their hospital stay.

Fourteen days post-randomization

Primary endpoint ascertainment

Thirty days post-randomization

Secondary endpoint ascertainment

Statistical Plan

Sample Size Determination

:

In our retrospective analysis of patients with AKI at 3 potential study hospitals, the composite outcome of death, dialysis, and progression of AKI was 24.5% (of 29,027 individuals with AKI). We believe a clinically meaningful relative reduction in this risk would be 20%, leading to an absolute rate of 19.6% in the intervention group. By enrolling 5,024 patients (2,512 in each group), we would have 90% power to detect a difference in outcome at least this extreme at a two-sided alpha of 0.05 as calculated using the Cochran-Mantel-Haenszel test (accounting for 6 hospital strata). We have elected to increase this number by 20% to account for potential contamination of the effect across

study arms, leading to a final sample size of 6,030 individuals. This sample size will also allow us to detect at least a 16% increase in best practices measures in the intervention group.

We must also consider that patients enrolled once in the trial will be excluded from enrolling again (on another admission, for example). While we don't have data on the rates of recurrent AKI we estimate that up to 20% of eligible patients may be excluded on this basis, which may slow recruitment somewhat.

In addition, pauses in trial enrollment may occur due to protocol changes / amendments based on feedback from providers and for quality improvement activities.

As such, we expect active enrollment, data acquisition, and outcome assessment to be completed over a three-year period.

Statistical Methods

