The primary analysis will utilize the intention to treat principle. The primary outcome (a composite of progression of AKI, dialysis, and death) will be compared across the groups using the Mantel-Haenszel chi-square test for correction for the 6 study strata (by hospital). Statistical significance will be based on a p-value of <0.05.

In addition, a retrospective examination will be performed to assess improvement in the control group before / after intervention as a measurement of contamination. We expect that providers who receive AKI alerts on some patients may be more likely to look for AKI in other patients, potentially diluting the effect of the intervention – this pre/post intervention analysis will help in assessing that level of contamination.

Because we are enrolling patients across six sites, we will do an exploratory analysis to determine the efficacy of alerts independently at each hospital.

We have specified several subgroups in whom the benefit of an AKI alert may differ from the general population. These groups will be analyzed as secondary and exploratory analyses. They include:

- Surgical patients
- Subjects with baseline creatinine <1.0mg/dl
- Subjects with baseline creatinine <0.5 mg/dl
- Females (due to lower rate of increase in creatinine after AKI)
- African Americans (due to higher rate of increase in creatinine after AKI)
- Elderly subjects (age > 65, age > 70, and age > 75)
- Subjects in an ICU at the time of the alert
- Subjects who enter the study based on relative vs. absolute creatinine criteria vs. both

Finally, as the academic year progresses, new clinicians (such as residents and interns) may become more facile in their ability to recognize AKI, which may attenuate the effect of this intervention. We will model this in exploratory analyses using an intervention-by-time of year interaction term in models of the primary outcome.

4. Genetic Testing N/A

A. Describe

- i. the types of future research to be conducted using the materials, specifying if immortalization of cell lines, whole exome or genome sequencing, genome wide association studies, or animal studies are planned
 - ii. the plan for the collection of material or the conditions under which material will be received
 - iii. the types of information about the donor/individual contributors that will be entered into a database
 - iv. the methods to uphold confidentiality

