We present descriptive statistics as median (interquartile range) for continuous variables and proportions for categorical variables. For the primary analysis, and all comparisons of categorical variables between the intervention and control group, we used the Mantel-Haenszel test, accounting for each hospital site as an individual stratum. The Mantel-Haenszel approach was used to obtain the pooled relative risks across hospital strata without adjusting for other baseline factors. As a sensitivity analysis, we used modified Poisson generalized estimating equations with a robust variance estimator to present the relative risk estimates adjusting for the following characteristics assessed at the time of randomization: age, sex, race, creatinine, blood urea nitrogen, white blood cell count, heart rate, respiratory rate, systolic and diastolic blood pressure, CHF, hypertension, diabetes, modified SOFA score, Elixhauser comorbidity score, and hospital.²⁻⁴ We used the Van Elteren test to compare continuous variables across the intervention groups, again accounting for hospital strata. To compare time-to-event between study groups, we used Cox proportional hazard regression with intervention as the independent variable, stratified by hospital, with censoring at 14-days after randomization. For individual hospital analyses, Kaplan-Meier curves were generated and log-rank tests were used. Patients discharged prior to 14 days without an outcome of interest were assumed to be free of that outcome at 14 days. Death was treated as a censoring event in analyses where death was not the outcome. We used Schoenfeld residuals to examine the proportional hazards assumption in Cox models; there were no violations.

We prespecified several secondary outcomes and subgroup analyses which we present without adjustment for multiple comparisons. We also pre-specified that each hospital would be analyzed

independently for evidence of heterogeneity of alert effects. Given the observed heterogeneity of effects, we explored mediators of that heterogeneity through the use of a generalized linear model in which the independent variables included an alert-by-hospital-type interaction term. Patient-level covariates were then added to this base model to determine if the significance of the interaction would be ablated by including these factors. Although patient characteristics did not account for the heterogeneous results, grouping hospitals into “teaching” vs. “non-teaching” did.

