Due to the unexpected finding of increased harm from the alert at non-teaching hospitals, we conducted several *post hoc* analyses, which are specifically identified in the results. To determine if the effect was mediated by actions downstream of the alert, we performed a formal mediation analysis using the method of Baron and Kenny (adjusted for age, sex, race, creatinine, blood urea nitrogen, white blood cell count, heart rate, respiratory rate, systolic and diastolic blood pressure, CHF, hypertension, diabetes, malignancy, modified SOFA score and Elixhauser comorbidity score at the time of randomization) of the following hypothesized mediators: markers of fluid overload, certain medications, the presence of renal consult, attending involvement in the care of the patient (as measured by the percent of alerts that went to attendings versus other providers), and the burden of other interruptive alerts (such as those for sepsis or medication interactions).^{5,6} The burden of other interruptive alerts was quantified as the number of other alerts received while the patient was eligible to be receiving AKI or Control alerts, divided by the amount of time they were eligible, leading to an average “non-aki alert per day” metric. Finally, we examined the rates of death and AKI progression in the time period 2 years prior to the start of the trial in each hospital to assess the degree of contamination across the study arms.

We assessed whether alert effectiveness changed over time by including an interaction term representing “time from first enrollment at this hospital” with the randomization status in a logistic regression equation. A significant p-value for this interaction term would suggest that the effect of the alert waxed or waned over time once it was “live” at a given hospital.

Our preliminary data suggested that 24.5% of patients would experience the composite outcome. We determined that a relative 20% reduction in this outcome (to 19.6) would be clinically significant. A sample size of 2,512 in each arm of the study achieves 90% power to detect this degree of change, but given the potential for contamination across study arms (whereby clinicians “learn” to identify and care for AKI over the course of the trial), which would tend to bias the results towards the null, we inflated the sample size by 20% to a total of 6,030.

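### Heterogeneity of the alert effect across the six hospitals is sought in separate hospital analyses; no joint alert-by-hospital test is named, and the one interaction fitted uses a grouping chosen afterwards

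*SAP*

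**What the plan says.** The protocol (section 3, Statistical Methods) states that, because there are six sites, "we will do an exploratory analysis to determine the efficacy of alerts independently at each hospital". The SAP (Outcome Measures and Statistical Analysis) repeats that the hospital analysis was prespecified and gives its purpose: each hospital is examined "independently for evidence of heterogeneity of alert effects. Given the observed heterogeneity of effects, we explored mediators of that heterogeneity". On method it says: "For individual hospital analyses, Kaplan-Meier curves were generated and log-rank tests were used".

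The SAP then describes a generalized linear model with an alert-by-hospital-type interaction. Patient covariates were added to see whether the interaction stayed significant, and the teaching/non-teaching grouping is said to account for the differing results. Post hoc analyses follow, prompted by unexpected harm at the non-teaching hospitals; they include a mediation analysis.

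Neither document names an alert-by-hospital interaction over all six sites, a Cochran Q or a Breslow-Day test. Teaching status is absent from the subgroup lists in protocol sections 3 and 12, the only such lists in the documents.

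**The concern.** A test within one hospital asks whether the effect there is zero. Six such tests do not ask whether the six effects differ. When each has modest power, one common effect will usually give a patchwork of results that looks like heterogeneity. The documents give no test that separates such a patchwork from real variation before moving on to explain it.

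The later interaction test does compare groups of hospitals. However, its grouping came after the hospital results, so its nominal p-value takes no account of that choice.

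At stake are the exploratory conclusions built in sequence on this step: that the effect differs by hospital, that teaching status explains it, and that harm at two hospitals has identifiable mediators. Those two hospitals hold 684 + 146 = 830 of the 6,031 patients in Box 1. A harm finding there could influence whether such alerts are used, so readers need to know whether the variation exceeds chance.

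**Working it through.** **Inputs.** The control rate comes from the protocol (section 3, Sample Size Determination): "the composite outcome of death, dialysis, and progression of AKI was 24.5% (of 29,027 individuals with AKI"). The design effect is a "relative reduction in this risk would be 20%, leading to an absolute rate of 19.6% in the intervention group", so RR = 19.6/24.5 = 0.8. Hospital sizes are from SAP Box 1: 2515, 1248, 935, 503, 684 and 146 (sum 6,031).

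Assumptions, because the documents do not give these: the control rate is 24.5% in every hospital, each hospital splits 1:1, each hospital is tested at two-sided 0.05, and a 14-day binary comparison stands in for the log-rank test.

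**The plan's own figure.** No figure is given for the heterogeneity analysis. The only power statement is the overall one: "By enrolling 5,024 patients (2,512 in each group") for "90% power to detect a difference in outcome at least this extreme at a two-sided alpha of 0.05". The pooled-variance two-proportion formula gives 1,503 per arm from these inputs, and 2,512 per arm gives 98.7% power, so the stated size is not reproduced. The stratum inputs to the plan's calculation are not given. The difference is toward more power and does not bear on this point.

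**Step 1: power within each hospital.** With m = n/2 per arm and p̄ the mean of the two rates,

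power = Φ[(p1 − p2 − 1.96·√(2p̄(1−p̄)/m)) / √((p1(1−p1)+p2(1−p2))/m)].

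For hospital 1, m = 1257.5: (0.049 − 1.96 × 0.01653)/0.01650 = 1.005, so power is 84%. For hospitals 1 to 6 at RR 0.8: 84, 55, 44, 26, 34 and 11%. At RR 0.9: 31, 17, 14, 10, 11 and 5%.

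**Step 2: chance of a mixed pattern under one common effect.** P(mixed) = 1 − Π(power) − Π(1 − power).
- RR 0.8: 1 − 0.0019 − 0.0173 = 98.1%.
- RR 0.9: 1 − 0.000004 − 0.3728 = 62.7%.
- RR 1.0: 1 − 0.95^6 = 26.5% for at least one significant hospital; all six together is negligible. Simulation gives 25%.

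**Step 3: is unequal size the cause?** 40,000 simulated trials per setting, log RR in each hospital, Box 1 sizes against six hospitals of 1,005:

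| Common RR | Mixed, Box 1 sizes | Mixed, equal sizes | Some estimate above 1, Box 1 | Some estimate above 1, equal |
|---|---|---|---|---|
| 0.8 | 97.9% | 96.5% | 39% | 17% |
| 0.9 | 62.6% | 61.8% | 77% | 69% |
| 1.0 | 25.3% | 26.1% | 98% | 99% |

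Unequal size barely changes the mixed-significance pattern. At RR 0.8 it does spread the point estimates.

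**Step 4: significant harm in at least one hospital.** With no effect anywhere, 1 − 0.975^6 = 14.1% (13.3% simulated). Simulated at a common RR of 0.9: 2.1%; at 0.8: 0.4%.

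**Step 5: choosing the grouping afterwards.** Simulated with identical effects in all hospitals:
- teaching split fixed in advance: about 5% significant;
- better of the two binary attributes in Box 1 (academic, location): about 8%;
- best of three, adding hospitals 1 and 2 (shared staff) against the rest: about 11%;
- best of all 31 two-group splits: 39%.

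**Step 6: the joint test.** Q = Σ wᵢ(θᵢ − θ̄)², with θᵢ the hospital log RR and wᵢ its inverse variance, referred to chi-square on 5 df. With a common RR of 0.8, 0.9 or 1.0 it is significant in about 4.5% of trials. Under assumed real heterogeneity (RR 1.0 at teaching hospitals), its power is about 23% if the non-teaching RR is 1.25 and 76% if it is 1.5. The 1-df teaching contrast has 43% and 93%.

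**The case against.** The strongest reply is that the SAP does not say heterogeneity was read off a mix of significant and non-significant log-rank tests. Hospital-level effects are prespecified, 95% intervals are promised throughout, and p-values for secondary and exploratory analyses are withheld except for safety outcomes. The analysis may have rested on estimates. This is fair, and it rules out claiming to know how the judgement was made. But six intervals read side by side are not a test of difference either, and the SAP does use the significance of an interaction to decide what explains the variation.

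A second reply is that a formal interaction is present and that its split is natural: hospitals 5 and 6 are the two non-teaching sites and share personnel. For a true teaching difference it is also more powerful than the 5-df test. All this stands. A reader might infer that the plan has no between-hospital comparison at all; that would be wrong. A reader might also take 39% as the error rate. It is an upper bound, because no search over all splits is described. What remains is that the contrast followed the observed results, with no global test before it.

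Third, the work is labelled exploratory, the SAP warns that inferences from the unadjusted intervals may not be reproducible, and a joint test added now would itself come after the data. These points limit the severity. They do not supply the missing test, and the question it answers, whether effects differ by hospital, was prespecified.

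**Conclusion.** The point holds in a limited form. Heterogeneity is sought by separate analyses that cannot establish it; no joint six-hospital test is named; and the only interaction uses a grouping adopted after the results. Disagreement between hospitals is close to certain under a common RR of 0.8 (98%), more likely than not at 0.9 (63%), and occurs in about a quarter of trials with no effect. Post hoc choice of grouping takes the interaction's error from 5% to roughly 8 to 11% under two or three candidate groupings.

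Two stronger readings are tempting and not supported. One is that the unequal hospital sizes produce the apparent heterogeneity: equal hospitals give nearly the same mixed pattern, and low power with six looks is the main cause. The other is that the harm at non-teaching hospitals is an artefact. A common benefit would rarely give a significant harm signal anywhere (0.4 to 2%), and even with no effect the chance is about 14%. The harm may be real; the plan as written does not test properly whether it differs from the effect elsewhere.

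The figures rest on the assumptions listed with the inputs. The stratified Mantel-Haenszel primary analysis is unaffected. This should be changed, but it does not threaten the main result.

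**What to change.** Make one joint alert-by-hospital test on the primary composite the heterogeneity analysis: 5 df, either as an interaction in the relative-risk model or as Cochran Q on the six log RRs. Report its p-value, the between-hospital variance with a confidence interval, and the six hospital RRs with 95% intervals. Keep the per-hospital Kaplan-Meier curves as display only, not as evidence that effects differ. Label the teaching/non-teaching interaction as post hoc and state that its nominal p-value does not account for the choice of grouping. State also that the joint test was added after the data were seen, if that is so.

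The cost is some SAP wording and a few lines of code on data already held. The drawback is limited power (23% and 76% in the two scenarios above), so a non-significant joint test must not be read as homogeneity, and the variance estimate should be reported whatever the p-value. The heterogeneity claim may come out weaker. Search-adjusted p-values and shrunken hospital estimates are optional additions.

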Electronic Alerts for Acute Kidney Injury Amelioration (ELAIA-1)

NCT Title and ID: Optimizing Electronic Alerts for Acute Kidney Injury

NCT02753751

August 21, 2020

Supplementary Methods

Trial Design and Oversight

A detailed description of the trial design and rationale was previously published.¹ Briefly, we conducted an individual level, parallel-group, randomized controlled trial of AKI EHR alerts versus usual care in hospitalized adults. While patients and providers could not be masked to the intervention, study investigators and analysts were masked to study group assignments until data collection and primary analysis were complete.

The trial was conducted in accordance with the principles of the Declaration of Helsinki and two institutional review boards associated with the six study hospitals approved the study that was deemed minimal risk. Patients were enrolled under a waiver of informed consent, as the alert was deemed unlikely to infringe on patient welfare and informing patients of their AKI diagnosis would contaminate the usual care group. An external data and safety monitoring board performed four independent assessments during the trial, including one formal interim analysis. This trial was registered with clinicaltrials.gov under registration number NCT02753751 prior to study initiation.

Patients

Inpatients adults ≥ 18 years with AKI as defined by the Kidney Disease: Improving Global Outcomes (KDIGO) as an increase in creatinine 0.3 mg/dl within 48 hours or 1.5 times the lowest measured creatinine within the prior 7 days of hospitalization were eligible. We did not use creatinine values >7 days prior to admission in order to avoid including patients with rapid progression of chronic kidney disease, but not AKI. Due to missing and inaccurate urine output data, urine output was not used to classify AKI. Inpatients were enrolled at 6 hospitals within a large health system (Box 1). Hospitals 1 and 2 share personnel, as do hospitals 5 and 6. Hospitals 3 and 4 are largely independent in terms of staffing. The hospitals range from 60 – 1030 beds. Hospitals 1-3 are urban, academic teaching hospitals.

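### If patient covariates entered only as main effects, the model cannot separate patient mix from hospital type, so ruling out patient characteristics is unsupported

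*SAP*

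**What the plan says.** In the SAP, Statistical Analysis, the difference in alert effect between hospitals is explored "through the use of a generalized linear model in which the independent variables included an alert-by-hospital-type interaction term". The next step is: "Patient-level covariates were then added to this base model to determine if the significance of the interaction would be ablated by including these factors". The conclusion follows: "Although patient characteristics did not account for the heterogeneous results, grouping hospitals into" teaching and non-teaching did.

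For this step the SAP does not list the covariates, give their form or name the link. The same section lists 15 patient characteristics, plus hospital, for the adjusted sensitivity analysis ("adjusting for the following characteristics assessed at the time of randomization: age, sex, race, creatinine, blood urea nitrogen" and ten more). The covariate list for the mediation analysis adds malignancy, making 16 ("hypertension, diabetes, malignancy, modified SOFA score and Elixhauser comorbidity score at the time of randomization").

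The mediation and other post hoc work comes next and is introduced with "Due to the unexpected finding of increased harm from the alert at non-teaching hospitals". On staffing, the SAP (Patients) says: "Hospitals 1 and 2 share personnel, as do hospitals 5 and 6". Hospitals 5 and 6 are the two non-teaching sites.

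The Protocol (section 3, Statistical Methods, and again in section 12) names patient subgroups and says: "These groups will be analyzed as secondary and exploratory analyses".

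**The concern.** Two explanations compete. Non-teaching hospitals may use the alert differently, or they may treat more patients of a kind for whom the alert does harm. The second is effect modification by a patient trait, and testing it requires the trait to interact with the alert. As described, only hospital type was given that role.

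A covariate main effect describes who is at higher risk, not in whom the alert works differently. Under patient-level randomisation it is nearly unrelated to the alert-by-type term, so a surviving interaction is the expected result under either explanation.

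Loss of significance is also a weak yardstick, because it mixes a change in the estimate with a change in its standard error.

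At stake is a declarative sentence that sets patient mix aside just before the SAP examines harm at non-teaching hospitals. A reader would take patient mix as tested.

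**Working it through.** The documents give no interaction estimate or p-value, so there is no plan figure to reproduce. The check asks whether the described step can distinguish the two explanations.

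**Inputs from the documents.** SAP Box 1: teaching 2,515 + 1,248 + 935 + 503 = 5,201; non-teaching 684 + 146 = 830; total 6,031, of which 830 is 13.8%. SAP, Patients: simple randomisation of individual patients.

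**Assumptions.** Control risk is 20%. A binary trait is present in 25% of teaching patients and in 70%, 45% or 35% of non-teaching patients.
- Truth A: the trait is the sole cause (alert RR 1.45 with it, 0.90 without).
- Truth B: hospital type is the sole cause, set to the same RRs by hospital type as A.

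**Why a main effect cannot help.** Take a log-link Poisson model, log risk = a + bA + cH + dAH + eX (A alert, H non-teaching, X trait). Its score equations make fitted and observed events agree in each of the four arm-by-type cells. The fitted total in a cell is n × exp(a + bA + cH + dAH) × mean of exp(eX). Randomisation makes that mean the same in both arms within a hospital type, so it cancels from the RR. Then exp(d) is the ratio of the crude RRs whatever e is, apart from chance arm imbalance.

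**Expected values under A.** RR = 0.90(1 − p) + 1.45p.
- p = 0.25: 0.675 + 0.3625 = 1.0375
- p = 0.70: 0.270 + 1.015 = 1.285; ratio 1.285/1.0375 = 1.24
- p = 0.45: 0.495 + 0.6525 = 1.1475; ratio 1.11
- p = 0.35: 0.585 + 0.5075 = 1.0925; ratio 1.05

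Ratio of RRs in three nested models (base / plus trait / plus alert-by-trait):

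| Trait, non-teaching vs teaching | A: trait is the cause | B: hospital type is the cause |
|---|---|---|
| 70% vs 25% | 1.24 / 1.24 / 1.00 | 1.24 / 1.24 / 1.24 |
| 45% vs 25% | 1.11 / 1.11 / 1.00 | 1.11 / 1.11 / 1.11 |
| 35% vs 25% | 1.05 / 1.05 / 1.00 | 1.05 / 1.05 / 1.05 |

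**The SAP's criterion, by simulation** (10,000 trials per scenario, modified Poisson with robust variance). The last two columns are shares of trials whose base interaction was significant in the harm direction.

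| Trait | Base p<0.05 (A, B) | Still significant after main effect (A, B) | Still significant after alert-by-trait (A, B) |
|---|---|---|---|
| 70% vs 25% | 33.4%, 33.4% | 97.5%, 99.6% | 6.4%, 78.4% |
| 45% vs 25% | 11.2%, 10.9% | 95.3%, 99.4% | 25.4%, 87.5% |
| 35% vs 25% | 6.4%, 6.6% | 96.5%, 99.3% | 52.0%, 93.5% |

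The main-effect step gives nearly the same answer under both truths. Under A it removes on average 0.1% to 0.4% of the log ratio (95% of trials within about −5% to +6%).

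Among the selected trials under A, adding alert-by-trait moves the mean ratio from 1.44 to 1.16, 1.43 to 1.29 and 1.43 to 1.36 (58.7%, 28.5% and 14.8% of the log ratio). It does not reach 1.00 because selecting on significance also selects chance. Under B the ratio does not move on average, yet at 70% vs 25% 100 − 78.4 = 21.6% of significant interactions lose significance. That is the weakness of the yardstick.

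**Hand check of the base model at 70% vs 25%.** Var(log RR) is the sum over arms of (1 − risk)/(n × risk).
- Non-teaching, 415 per arm: 0.800/83.0 + 0.743/106.7 = 0.0166
- Teaching, 2,600.5 per arm: 0.800/520.1 + 0.7925/539.6 = 0.0030
- SE = √0.0196 = 0.140, so the 95% CI is about ×/÷ exp(1.96 × 0.140) = 1.32
- log 1.24 = 0.214; 0.214/0.140 = 1.53; power is about Φ(1.53 − 1.96) = 33%, agreeing with the simulation

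**Sensitivity.**
- If the trait also raises control risk 1.3-fold, the interaction under A stays significant after the main effect in 96%, 92% and 86%.
- With a logit link, the odds ratios under A are 1.32/1.32/1.00, 1.14/1.14/1.00 and 1.07/1.07/1.00.
- A different set of assumptions (prevalence 80% vs 20%, control risk 18% without the trait and 1.3 times that with it, alert RR 1.5 with it and 0.95 without) gives logit coefficients of 0.369, 0.372, 0.000 under A and 0.369, 0.370, 0.363 under B.

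**The case against.** - **The SAP does not say main effects.** True. If alert-by-covariate terms were fitted, the objection falls and a sentence stating so settles it. But hospital type is the only factor described as interacting with the alert.
- **The step is not empty.** It addresses chance imbalance between arms, a real rival explanation with only 830 non-teaching patients. That stands; the fault is that the conclusion is broader than the step.
- **Other evidence bears on patient mix.** Box 1 shows similar medians for non-teaching and teaching hospitals (SOFA 2, 2 vs 2, 1, 2, 2; Elixhauser 7, 7 vs 6, 6, 7, 6), which makes those two scores less likely explanations. The Protocol subgroups cover age, sex, race and creatinine, plus surgery, ICU and entry criterion. A strong single modifier there would probably show: a plain alert-by-trait test finds the assumed trait in 99% of simulated trials. But 15 − 4 = 11 listed characteristics are not among those subgroups, and the subgroups are taken one at a time without a link to hospital type.
- **The sizes are hypothetical.** The 70% vs 25% case is an imbalance of about 1.0 SD. At 35% vs 25%, about 0.22 SD, the base interaction is significant in only 6.4% of trials, close to chance, and patient mix could explain little. This limits the practical weight, not the structural point.
- **It is exploratory and carries caveats.** The SAP warns about unadjusted intervals and reproducibility, but that warning concerns multiplicity. The mediation analysis adjusts for patient characteristics but asks about actions after the alert.

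**Conclusion.** The concern holds, on the condition that the covariates entered as main effects. On that reading the step returns almost the same result whether patient mix or hospital type is the cause, and excluding patient characteristics is unsupported by it. It is not shown to be false.

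The non-movement follows from randomisation and does not depend on the assumed trait. How much patient mix could explain does depend on it: in the illustration, a ratio of RRs from 1.05 to 1.24. The documents do not give the actual imbalance, and apart from the two Box 1 scores no covariate is shown by hospital.

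The consequence is confined to how the harm at non-teaching hospitals is explained. The primary analysis is unaffected.

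**What to change.** 1. State the covariates, their form and the link. Refit with main effects and alert-by-covariate interactions for the 15 patient characteristics listed in the SAP. Report the alert-by-hospital-type ratio of RRs with its 95% CI before and after, and judge the change in the estimate with a bootstrap CI, not by loss of significance. Keep the exclusion of patient characteristics only if this model supports it; otherwise write that patient mix could not be ruled out.
2. Label the teaching split as post hoc and resting on two hospitals (830 of 6,031 patients) that share personnel. This is minor. The SAP says that post hoc analyses are identified in the results, which are not among these documents, so the label may already be there.

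**Cost.** One refit on data already collected and two sentences. With an assumed shift of 0.1 to 0.3 SD per covariate between hospital types, the standard error of the interaction rises by about 0.3% to 3% if the 15 covariates are correlated at 0.2, or 1% to 9% if they are independent. The interval is wide either way (about ×/÷1.32 before and ×/÷1.34 after in the 70% vs 25% illustration), so the refit may support only the weaker wording. With hospital type the sole cause, noise alone can move the log ratio by about −31% to +30% at 70% vs 25%, and by about 7% either way at 35% vs 25%. That is why the change needs its own interval.
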